8.2.6 Coefficient of Variation

• Computation of the Endpoint

The coefficient of variation is a measure of relative variability, calculated as:

• Coefficient of Variation = $\frac{\sqrt{\frac{\sum (m_i - \bar{x})^2}{n-1}}}{\bar{x}}$, where $\bar{x} = \frac{\sum m_i}{n}$, and m_i is the i^{th} measurement per organ per subject. There are expected to be i=6 measurements for each visit per organ per subject. Analysis of the Endpoints

Summary tables with descriptive statistics for the coefficients of variation for SUVmax and SUVpeak by organ will be produced by visit.

8.3 Examination of Subgroups

The repeatability coefficients, Bland-Altman plots, and intraclass correlation coefficients described in section 8.2 will be repeated by amyloid type: (AL versus ATTR).

9 SAFETY EVALUATION

The secondary study objective is to characterize the safety and tolerability of repeat doses of ¹²⁴I-AT-01 administered by IV infusion or slow IV bolus. The key secondary endpoints are incidence of treatment-emergent AEs from Day 1 to EOS, change from baseline in clinical laboratory values at Visits 2 and Safety Follow-up 1 (1-3 days after the second infusion), change from baseline in vital signs, and change from baseline in anti-drug antibodies (ADA).

Change from baseline in ADA is outside the scope of this SAP.

9.1 Overview of Safety Analysis Methods

The safety analyses will be performed for the Safety Set and will include treatment-emergent adverse events (TEAEs), serious adverse events (SAEs), vital signs, biomarkers, and concomitant medications. Tabular summaries of descriptive statistics will be presented for all subjects included in the Safety Set.

For all safety endpoints, baseline will b

e the last non-missing value before administration of ¹²⁴I-AT-01.

Safety data will not be imputed, except for partial and missing dates, which will be imputed only for defining TEAEs and concomitant medications. Imputed dates will not be presented in data listings.

Partial dates will be imputed for the purposes of defining TEAEs as follows:

- For a missing start day where the month and year are present, the start day will be set to the first day of the month, unless 1) the first day of the month is before the most-recent date of administration of ¹²⁴I-AT-01 and the month and year are the same as the month and year of the most-recent date of administration of ¹²⁴I-AT-01, and 2) the end date is on or after the most-recent date of administration of ¹²⁴I-AT-01or the end date is completely missing, in which case the start day will be set to the most-recent date of administration of ¹²⁴I-AT-01.
- For a missing start day and month where the year is present, the start day and month will be set to January 1st, unless 1) January 1st is before the most-recent date of administration of ¹²⁴I-AT-01 and the year is the same as the year of the most-recent date of administration of ¹²⁴I-AT-01, and 2) the end date is on or after the most-recent date of administration of ¹²⁴I-AT-01 or the end date is completely missing, in which case the start day and month will be set to that of the most-recent date of administration of ¹²⁴I-AT-01.
- For a missing end day where the month and year are present, the end day will be set to the last day of the month, unless the month and year are the same as the month and year of the last contact date for the subject, in which case the end day will be set to that of the subject's last contact date.
- For a missing end day and month where the year is present, the end day and month will be set to the subject's last contact date, unless the year of the subject's last contact date is

Page 21 of 38

greater than the end year, in which case the end day and month will be set to December $31^{\rm st}$.

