9.3 Sample Size Determination

A formal sample size calculation is not provided for this study. The sample size of up to 20 subjects was estimated based on systematic literature review analysis sets.

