10.5 Appendix 5: Protocol Amendment History

The amendment history for Protocol AT01-001 is provided in Table 3.

Table 3: Protocol AT01-001: Amendment History

| Version | Version Date | Brief Description | |
|---------|-------------------|--|--|
| 2.0 | 08 March 2022 | Revisions from Version 1.1 include the following: | |
| | | Addition of slow IV bolus at 1 mL/5 seconds as a method of administration. | |
| | | Updated clinical experience to reflect final results from Study AMY1001. | |
| | | Minor administrative and editorial revisions. | |
| 1.1 | 07 October 2021 | Revisions from Version 1.0 include the following: | |
| | | • Addition of heparin/heparin analogs as a prohibited concomitant medication within 7 days of infusion of ¹²⁴ I-AT-01. | |
| | | Minor administrative and editorial revisions. | |
| 1.0 | 27 September 2021 | Original protocol; used for pre-submission activities. This version was not submitted to any health authorities or IRBs/ECs, nor was it implemented. | |

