3.2 Study Objectives

The primary study objective is to evaluate the repeatability of organ-specific quantitation of radiotracer uptake following PET/CT imaging of ¹²⁴I-AT-01 in subjects with AL or ATTR systemic amyloidosis.

The secondary study objective is to characterize the safety and tolerability of repeat doses of ¹²⁴I-AT-01 administered by intravenous (IV) infusion or slow IV bolus.

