3.3 Study Design

This is a multicenter, open-label, single arm study in subjects with AL or ATTR systemic amyloidosis. ¹²⁴I-AT-01 is the only study intervention; neither reference therapy nor placebo will be administered.

This study consists of a screening period of up to 30 days; two, one-day treatment periods (Day 1 and Week 6); a safety follow-up 1-3 days after the second administration of 124 I-AT-01, and a final safety follow-up 28 ± 3 days after the second administration of 124 I-AT-01. Thus, the total subject duration is approximately 14 weeks. A study flow chart is provided in appendix 14.1 and a schedule of events is provided in appendix 14.2.

A formal sample size calculation is not provided for this study. The sample size of up to 20 subjects was estimated based on systematic literature review analysis sets.

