8.1.4 Multiple Comparisons/Multiplicity

No adjustments for multiple comparisons will be made. Any p-values will be considered descriptive.

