9.2 Extent of Exposure

Only subjects enrolled in this study may be treated with ¹²⁴I-AT-01. During the study, qualified clinical site staff will administer all study drug. The date and time for each dose will be recorded in the CRFs.

The actual dose of ¹²⁴I-AT-01 will be summarized in mCi and mg by study visit. The administration type (infusion, IV bolus), duration of administration (for infusions) and number of subjects experiencing an administration interruption and associated reason for interruption will be summarized by study visit.

 124 AT-01 compliance is defined as receiving 1 mCi (+/- 10%) (<= 2mg 124 AT-01). KI compliance is defined as receiving KI orally for 3 days in the specified time periods. The number of and percent of compliant subjects for 124 AT-01 and for KI will be summarized by visit.

A listing of all administrations of ¹²⁴I-AT-01 will be provided by subject and visit.

A listing of all administrations of potassium iodide (KI) will be provided by subject and visit.

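### The planned safety outcome tables pool the 2-5 minute infusion with the slow IV bolus, so a reaction rate specific to the bolus would be diluted and recoverable only from by-subject listings

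*SAP*

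**What the plan says.** Version 2.0 of the protocol lists as a change "Addition of slow IV bolus at 1 mL/5 seconds as a method of administration" (Protocol 10.5). The study schema and schedule of activities (Protocol 1.2 and 1.3) tie method to protocol version: infusion for Version 1.1, bolus for Version 2.0. They also require the same method at Week 6 as on Day 1.

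The secondary objective is safety and tolerability of repeat doses "administered by intravenous (IV) infusion or slow IV bolus" (SAP 3.2).

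For the safety analyses, SAP 9.1 states that "Tabular summaries of descriptive statistics will be presented for all subjects included in the Safety Set". Method enters the tables in one place, the exposure summary: "The administration type (infusion, IV bolus), duration of administration (for infusions) and number of subjects experiencing an administration interruption" (SAP 9.2). SAP 9.4.1 plans day-of-dosing TEAEs by visit, system organ class and preferred term as the means of evaluating infusion-related reactions. SAP 9.4.3 adds hypersensitivity TEAEs and SAP 9.6 adds vital signs. None of these sections mentions method, and none of the corresponding titles in SAP 15.1 does. The only subgroup analysis, SAP 8.3, is by amyloid type and covers repeatability only.

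**The concern.** Method is a fixed subject-level attribute that the SAP already summarises. The amendment changed the rate of delivery, and infusion-related reactions are the first risk listed in Protocol Table 1. The earlier study described in Protocol 2.2.2 gave a single dose by IV infusion, and the documents report no earlier safety results for the bolus.

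Pooled tables would not show whether day-of-dosing events, hypersensitivity events or post-dose blood pressure changes arose with the bolus, the infusion or both. The greater risk is the reassuring case. If few or no reactions are seen, a pooled percentage and its implied precision will be read as applying to the bolus, when only some of the subjects received it.

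**Working it through.** The plan has no figure of its own to reproduce. It states "The sample size of up to 20 subjects was estimated based on systematic literature review analysis sets" (SAP 3.3), gives no formal calculation, and treats any p-value as descriptive (SAP 8.1.4). The calculations below are illustrations.

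**Inputs**
- Total N = 20, from the planned maximum. The Safety Set could differ, because Protocol 5.5 allows replacement.
- Bolus subjects: not given in either document. Assumed 5, 10 or 15 of 20.
- Product strength 0.1-1 mCi/mL and nominal dose 1 mCi (Protocol Table 2).
- Bolus rate 1 mL per 5 s; infusion 2-5 minutes, or 120-300 s.

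**1. Do the two methods differ in delivery time?**
- Undiluted volume = 1 mCi ÷ (0.1 to 1 mCi/mL) = 10 mL down to 1 mL.
- Bolus time = volume × 5 s/mL = 50 s down to 5 s, against 120-300 s.
- Table 2 permits dilution. The bolus would last as long as the shortest infusion only at 120 ÷ 5 = 24 mL or more. Below that volume the bolus is faster.

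**2. Dilution of a bolus-specific rate**
- If infusion subjects have no events, pooled rate = bolus rate × (bolus n ÷ 20). The factor is 1/4, 1/2 or 3/4 for 5, 10 or 15 bolus subjects.
- Example: three subjects react, all of them bolus subjects. Pooled, this is 3/20 = 15% (exact two-sided 95% CI 3-38%). For the bolus alone it is:
  - 3/5 = 60% (15-95%)
  - 3/10 = 30% (7-65%)
  - 3/15 = 20% (4-48%)

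**3. What zero events would show**

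One-sided 95% upper bound = 1 − 0.05^(1/n):

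| Group | n | Upper bound |
|---|---|---|
| Pooled | 20 | 13.9% |
| Bolus (assumed) | 15 | 18.1% |
| Bolus (assumed) | 10 | 25.9% |
| Bolus (assumed) | 5 | 45.1% |

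The exact two-sided 95% limits show the same pattern: 17% pooled, against 22%, 31% and 52% for 15, 10 and 5 bolus subjects.

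**4. Would a formal comparison help?**

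For assumed true rates of 30% (bolus) and 5% (infusion), exact Fisher power at two-sided 5% is 14%, 9% and 1% with 5, 10 and 15 bolus subjects. A test would be uninformative, so the case is for description only.

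**The case against.** Several objections have force.

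- **Method is not lost from the outputs.** The exposure table reports it. By-subject listings cover administrations (16.2.5.1), all AEs (16.2.7.1), day-of-dosing events (16.2.7.2 and 16.2.7.3) and vital signs (16.2.8.4). With about 20 subjects, a reader could match each reaction to its method. This stands: a signal would be diluted in the tables but recoverable. It does leave the by-method description to manual work after the data are seen.
- **Column layouts are not visible.** SAP 2 places table specifications in separate documents, and the sentence quoted from SAP 9.1 names a population, not a layout. The SAP 8.1.1 statement that data are summarised as a whole concerns sites. However, the titles in SAP 15.1 name other splits, such as visit and amyloid type, and never method. No SAP text calls for a method split, so pooling is the natural reading.
- **The objective is not unmet.** A reader might infer that pooling leaves the secondary objective unanswered for either method. The wording joins the methods with an or and states no comparison, and Protocol 9.1 has no hypothesis. A pooled description can satisfy it. What is missing is a description for each method.
- **Repeatability is not undermined.** A reader might extend the point to the primary endpoint. Method is constant within subject, so a change of method does not confound between-visit differences. On the undiluted figures, delivery times differ by at most 300 − 5 = 295 s, under 5 minutes, while the scan window is 5 hours ± 30 minutes. Pooling could only average over any difference in variance between methods, and nothing in the documents indicates one.
- **A split is weak evidence.** Method follows protocol version, so it is not randomised and is confounded with calendar time, and the counts are small. This stands, and it limits how the columns may be read. It does not favour the pooled figure as a description of the bolus.
- **Table 1 does not rank risks.** Infusion-related reactions come first, but Protocol 2.3.2 names tracer reactions and radiation together as the greatest risks.

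**Conclusion.** The point holds for the safety outcome tables: TEAEs, day-of-dosing TEAEs, hypersensitivity TEAEs and vital signs. As planned, they merge two delivery methods that the objective names and the SAP already records. A bolus-specific rate would be diluted by the bolus share of subjects, and a clean pooled result would suggest more certainty about the bolus than the data carry.

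The size cannot be fixed, because the documents do not give the split. At an assumed 5 to 15 bolus subjects of 20, the zero-event upper bound for the bolus is 45% to 18%, against 13.9% pooled. The 5-50 s delivery time assumes no dilution.

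This is a worthwhile, low-cost improvement in presentation. It is not a failure of the secondary objective and not a defect in the repeatability analysis.

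**What to change.** In SAP 9 and the table shells, add descriptive infusion, bolus and total columns to:
- the overall TEAE summary (14.3.1.1);
- the day-of-dosing tables (14.3.2.1, 14.3.2.2);
- the hypersensitivity table (14.3.2.4);
- the vital-sign tables (14.3.4.1, 14.3.4.2).

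Show method in the AE listings. State that no formal test will be made, and add a footnote that method is not randomised and is confounded with protocol version and calendar time.

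Marking method on the between-visit Bland-Altman plots is optional. SAP 9.2 summarises duration for infusions only. Add bolus volume and duration only if they are already collected, which the documents do not show.

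The cost is SAP and shell wording, using a variable the SAP already summarises. The downside is small per-method counts with wide intervals.

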9.3 Adverse Events

Adverse events will be coded using the Medical Dictionary for Regulatory Activities (MedDRA) Version 24.1 to identify the system organ class and preferred term. All AEs and SAEs will be recorded from the time of informed consent until the final EOS telephone follow-up (~Week 10).

Treatment-emergent AEs are defined as events that are newly reported or reported to worsen in severity after the start of treatment. Adverse events that occur after the treatment start date, occur on the treatment start date with a time that is equal to or after treatment start time, or that have a missing AE start date will be categorized as treatment-emergent. Treatment-emergent AEs will be summarized for the Safety Set.

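### Partial AE start dates are imputed against an undefined most-recent dose while TEAE status runs from dose 1, so on the natural reading some events after dose 1 leave the TEAE tables

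*SAP*

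**What the plan says.** SAP 9.1 allows one kind of safety imputation, for partial and missing dates, "which will be imputed only for defining TEAEs and concomitant medications". It has two start-date rules.

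- **Day missing:** "the start day will be set to the first day of the month, unless 1) the first day of the month is before the most-recent" administration. The exception also requires that "the month and year are the same as the month and year of the most-recent date of administration of" study drug, and "2) the end date is on or after the most-recent date of administration of" study drug or is completely missing. If all of this holds, the rule ends "in which case the start day will be set to the most-recent date of administration of" study drug.
- **Day and month missing:** "the start day and month will be set to January 1st, unless 1) January 1st is before the most-recent date of administration of" study drug, with a matching exception on the year and the end date.

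Neither rule mentions the first administration.

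SAP 9.3 defines TEAEs as "events that are newly reported or reported to worsen in severity after the start of treatment". It counts events after the treatment start date, events on that date with a time at or after treatment start, and those "or that have a missing AE start date will be categorized as treatment-emergent". Protocol 9.5.4 summarises only TEAEs. SAP 9 names TEAE incidence from Day 1 to EOS among the key secondary endpoints. Protocol 4.1.3.1 gives two administrations, at Day 1 and at Week 6 to Week 8, and Protocol 4.2.3 keeps them at least 6 weeks apart.

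**The concern.** The imputation exists to settle whether an event began before or after treatment started, so its reference date should be the start of treatment. The SAP instead uses the most-recent administration, which for anyone dosed twice is, on the natural reading, dose 2. The exception then does not look at dose 1, and the default (1st of the month, or 1 January) can push an event to before first exposure.

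The error runs one way for TEAE status: it can only remove events. It falls on the period after first exposure, and it is out of step with the SAP's other missing-data rules. A wholly missing start date counts as treatment-emergent (9.3), a missing grade as severe and a missing relationship as related (9.3.2), and a missing seriousness flag as serious (9.4). Knowing the month of onset can therefore make an event less likely to be counted than knowing nothing.

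**Working it through.** The documents give no figure to reproduce here, so the check applies the two rules to the dosing schedule.

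**Inputs.** Dose gap 42 to 56 days (Protocol 4.1.3.1 and 4.2.3); imputation rules (SAP 9.1); TEAE cut-off at dose 1 (SAP 9.3). Assumed for the enumeration: dose-1 dates on every day of 2022, true onset uniform from dose 1 to dose 2 + 28 days, and event length of 0, 2 or 7 days or end date missing.

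**Step 1: can the day-missing exception protect the dose-1 month?** Two dates in one month are at most 30 days apart, and 30 < 42, so the doses never share a calendar month. If most-recent is dose 2, an event in the dose-1 month never meets the month-and-year condition, whatever its end date.

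**Step 2: what happens in the dose-2 month?** The 1st is at most 30 days before dose 2, so it falls at least 42 − 30 = 12 days after dose 1. Such an event is a TEAE with or without the exception.

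**Step 3: example.** Dose 1 on 10 May 2022, dose 2 on 21 June (10 May + 42 days), true onset 12 May.

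| Recorded start | End date | Imputed start, last-dose anchor | TEAE? | Imputed start, first-dose anchor |
|---|---|---|---|---|
| May 2022 | 14 May | 1 May (9 days before dose 1) | No | 10 May |
| May 2022 | missing | 1 May | No | 10 May |
| 2022 | 14 May | 1 January | No | 10 May |
| 2022 | missing | 21 June | Yes | 10 May |
| wholly missing | any | none | Yes (9.3) | none |

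**Step 4: share of day-missing events affected.** In a month of L days, the pairs of dose-1 day and later-or-equal onset day in that month number L(L+1)/2. All are dated before dose 1 except the L pairs with dose 1 on the 1st. Over 2022 the pairs number 7 × 496 + 4 × 465 + 406 = 5,738, and (5,738 − 365)/5,738 = 93.6%. With 15 possible gaps, 5,373 × 15 = 80,595 of all 427,050 combinations of dose-1 date, gap and onset day are misdated, or 18.9%.

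**Step 5: day and month missing.** Across all onset days, 58.5%, 56.3% and 50.7% are dated before dose 1 for events lasting 0, 2 and 7 days, because an end date before dose 2 blocks the exception. With the end date missing the share is 4.3%, arising where dose 2 falls in the next calendar year.

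**Step 6: other anchors.** With the first administration as anchor, the share dated before dose 1 is 0% under both rules. It is also 0% if most-recent means the last dose before onset.

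These shares apply only to events with partial start dates in two-dose subjects. They are not estimates of how many TEAEs would be lost.

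**The case against.** The strongest reply is that most-recent is undefined and may mean the latest dose at the time of the event. SAP 9.5 uses the term relative to a reference point, and SAP 9.1 itself writes of a last contact date when it means a final one. On that reading the error vanishes. This stands as a limit on the finding, but it does not rescue the text. The onset date is the unknown quantity, analysis follows database lock (SAP 8.1.3), and two programmers could derive different TEAE tables. Sections 4, 6.1 and 6.4 refer to the first dose where that is meant.

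One could also argue that the 9.3 rule for a missing start date covers partial dates. That would leave the TEAE imputation in 9.1 without a purpose, so it is not the likelier reading.

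Four stronger inferences are tempting and should be resisted:

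- **That the exception protects only where it is not needed.** This is true of the day-missing rule. In the year-only rule, 1 January usually precedes dose 1, and the exception does keep events with a missing or late end date as TEAEs.
- **That each lost event costs 5% of incidence.** SAP 9.3.2 counts a subject once per category, so incidence moves only if the subject has no other TEAE there.
- **That the events disappear.** All reported AEs are listed (9.3.2), with separate listings for SAEs, withdrawals and deaths (9.4).
- **That swapping in the first dose costs nothing.** SAP 9.4.1 and 9.4.2 summarise TEAEs on dosing days and by period. If imputed dates feed those tables, a day-missing event in the dose-2 month that ended on or after dose 2, or has no end date, now goes to the dose-2 date. A first-dose anchor would put it on the 1st of that month, before dose 2. The current rule misplaces events too: among onsets after the dose-1 month and before dose 2, it moves 5.7% of 2-day and 18.3% of 7-day events onto the dose-2 date.

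**Conclusion.** The concern holds on the last-dose reading, and on any reading the anchor needs defining. Sections 9.1 and 9.3 do not contradict each other outright, since one handles partial and the other missing start dates. They use different reference dates for the same decision, and the less conservative result falls on the better-known date.

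For two-dose subjects with the day missing, every event in the dose-1 month is dated before dose 1 unless dose 1 fell on the 1st. With day and month missing, the loss is mainly of events that ended before dose 2. Subjects with one dose are unaffected because their most-recent dose is their first.

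The practical effect is probably small. The documents give no frequency of partial dates, and few are expected. One subject lost from a category changes its incidence by 1/20 = 5 percentage points, assuming about 20 in the Safety Set and no other TEAE for that subject in the category. Because the error favours the product on a key secondary endpoint and is cheap to remove, it should be corrected before database lock.

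**What to change.** 1. In both start-date bullets of SAP 9.1, replace the most-recent administration by the date of first administration at all four places in each: the comparison with the default date, the month-and-year (or year) match, the end-date comparison, and the imputed value.
2. State that an event imputed to the first-dose date, or recorded on that date with no time, is treatment-emergent. Without this, an imputed event has no time and, read literally, still fails the 9.3 test.
3. State that this imputation decides TEAE status only. Add one rule for how partial-date events are assigned in the day-of-dosing summary (9.4.1) and the by-visit summary (9.4.2), so that possible dose-2 events are not moved out of the dose-2 tables.

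The cost is a rewrite of two bullets, one sentence on missing times, and one extra rule for the two summaries. No additional data are needed.
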